11. STATISTICAL ANALYSIS

As stated, the primary outcome of this study is to demonstrate the feasibility of performing this type of trial in this patient population.

As a secondary aim, we anticipate being able to identify potential variables as primary endpoints for a larger study.

The principle investigators, project manager, and research coordinator will have access to data. Statistical analysis will be performed by [name].

Continuous variables will be compared using the Student's t-test. Categorical statistics will be compared using Chi-squared probability testing with Fischer exact modification when warranted by frequency observed. Both univariate and multivariate Cox models will be examined to determine the ability of clinical variables to predict the likelihood of clinical success or failure (i.e splenic salvage). A pre-determined p value of 0.05 was considered the threshold for statistical significance.

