4. AIMS AND OBJECTIVES

Aim 1: To demonstrate the feasibility of performing a trial of pSAE in trauma patients with splenic injuries (see section 8 “Outcomes”).

Objective 1a: To demonstrate that at least 50% of eligible patients can be enrolled into a randomized clinical trial.

Objective 1b: To demonstrate that successful follow-up at 30 days will be obtained in at least 80% of enrolled patients.

Aim 2: To evaluate clinical outcomes in order to identify endpoints for a larger trial (see section 8 “Outcomes”).

[figure not shown]
Objective 2a: To compare clinical outcomes of pSAE using coils versus vascular plugs.

Objective 2b: To compare technical outcomes of pSAE using coils versus vascular plugs.

Objective 2c: To conduct a cost analysis of using coils versus vascular plugs.

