- c) Signs of accompanying vascular injury such as pseudoaneurysm, extravasation, arterio-venous fistula, or hemoperitoneum
- d) Presence or absence of other intra-abdominal or extra-abdominal trauma

The following data points will be collected while the patient is admitted after the embolization procedure:

- a) Amount of blood products required

- b) Length of stay (ICU, floor, and total)
- c) Delayed complications (Abscess, bleeding, infarction, acute kidney injury)
- d) Secondary splenectomy (i.e. splenectomy needed after embolization)

The following data points will be collected at the 30 day follow up:

- a) Delayed complications (Abscess, bleeding, infarction, acute kidney injury)
- b) Secondary splenectomy

...

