13. HUMAN SUBJECTS RESEARCH

13.1 FDA Requirements

This study will enroll 50 patients with splenic injuries. The study interventions are approved by the Food and Drug Administration (FDA) as a Class 2 under 21 CFR 892.1600. Because it is a nonsignificant risk device being used in accordance with its defined indications, an FDA Investigational Device Exemption (IDE) is not required.

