14.3.2 Anticipated serious adverse events/serious adverse device effects (SADE)

Anticipated adverse device effects include:

- a) non-target embolization (<1%)
- b) migration of the coil or vascular plug (<1%)
- c) ineffective treatment requiring splenectomy (~10%)
- d) injury at the vascular access site (~1%)
- e) splenic infarction/splenic abscess (~3%)
- f) vessel rupture

Anticipated serious adverse events include:

- a) Given that iodinated contrast is used during the procedure, there is a very low risk for nephrotoxicity or allergic reaction to contrast (~1%).

Anticipated serious adverse events and adverse device effects will also be recorded using the "ELSA Adverse Event Recording Form". In addition, a "ELSA Serious Adverse Event/Serious Adverse Device Effect" form must be completed, and emailed to the ELSA Trial Office within 48 hours. All reports of anticipated serious adverse events/SADE will be forwarded to the medical monitor.

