14.4 Role and responsibility of the Independent Medical Monitor

Independent medical monitors will review all adverse events/effects and provide an unbiased written report of the events. At a minimum, the medical monitors must comment on the outcomes of the event or problem and in case of an serious adverse event/serious adverse device effect, comment on the relationship to participation in the trial.

If the death is considered unexpected and is either suspected or probably due to treatment, this event will be promptly reported to the medical monitor, who must indicate

whether he/she concurs with the details of the report provided by the principal investigator.

[name] (Division Chief, Acute Care Surgery) is the independent medical monitor for this study. He has committed to comply with the following statements:

The monitor:

- a) Is independent of the research team.
- b) Possesses sufficient educational and professional experience to serve as a subject advocate.
- c) Will promptly report discrepancies or problems to the IRB.

All follow up data to be collected while the patient is at UAB Hospital would already be collected, regardless of study participation. Again, data collected during the course of the research will be kept strictly confidential and accessed only by members of the trial team. Participant's details are stored within REDCap, a secure database used throughout the institution. Regular checks and monitoring are in place to ensure compliance. The data manager (in collaboration with the principal investigators) manages access rights to the data set. Participants are allocated an individual specific trial number and their details are anonymized. Regarding patient follow-up, the study doesn't require that the patient participate in any additional follow up than they would otherwise do if not enrolled in the study. The research coordinator will supplement follow up by making inquiries into the patient's subsequent condition at 30 days through the patient's chart. If no follow up is documented in the chart, then the research coordinator will attempt to conduct a telephone interview with the patient. However, we recognize that patients may drop-out of the study due to lack of follow-up. We will plan to continue enrolling patients until we have at least three months of post-procedure follow-up on the requisite 25 patients in each arm.

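### Section 11 plans multivariate Cox models for splenic salvage on about 5 expected splenectomies; the hazard ratios would be very imprecise and, with binary covariates, often not estimable

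*Combined protocol and SAP*

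**What the plan says.** Section 11 states: "Both univariate and multivariate Cox models will be examined to determine the ability of clinical variables to predict" clinical success or failure, which it equates with splenic salvage. It gives no list of covariates, no maximum number, no small-sample method and no fallback if a model cannot be fitted. It does not call the models exploratory. The next sentence reads: "A pre-determined p value of 0.05 was considered the threshold for statistical significance".

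The inputs that decide whether such models can work are elsewhere:

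- Section 13.1: "This study will enroll 50 patients with splenic injuries". Sections 8 and 10 give 25 per arm.
- Section 14.3.2 lists "ineffective treatment requiring splenectomy (~10"%) among the anticipated device effects. It is the only splenectomy rate in the document. It is not split by arm, has no stated time window and is not offered as a design assumption.
- Section 9 defines the event: "Secondary splenectomy (i.e. splenectomy needed after embolization"). It is recorded during admission and again at 30 days.
- Section 8, objective 1b, aims for follow-up in at least 80% of enrolled patients.
- Section 7.5 sets follow-up at 30 days, plus or minus 3. Section 14.4 plans to "continue enrolling patients until we have at least three months of post-procedure follow-up" on 25 patients in each arm.

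Feasibility is the primary outcome. The secondary aim in section 11 is to "identify potential variables as primary endpoints for a larger study"; section 4 puts Aim 2 as "To evaluate clinical outcomes in order to identify endpoints for a larger trial".

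**The concern.** In a Cox model the information comes from the number of events, not the number of patients. If only a handful of spleens are lost, a model with several covariates can fail in two ways. It may have no finite solution, because every splenectomy falls on one side of a covariate. Or it may converge to a hazard ratio that is large by chance. At stake is what the pilot hands to the larger trial: a predictor table with hazard ratios of 3 or more could be taken as a lead when there is nothing behind it.

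**Working it through.** **1. The plan's own figure.** Section 10 takes about 100 embolizations a year and a 50% enrolment goal: 0.50 x 100 = 50 = 2 x 25. This reproduces. It is a recruitment target; the plan has no event or power calculation.

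**2. Expected splenectomies.**

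- 50 x 0.10 = 5. The binomial 2.5% and 97.5% points are 1 and 9.
- If only the 80% goal is met: 0.80 x 50 = 40 followed, and 40 x 0.10 = 4 (range 1 to 8).
- If the rate were 5% (assumed): 2.5. If 20% (assumed): 10.

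**3. Precision for one balanced binary covariate.** SE(log HR) = sqrt(4/d) for d events, and the 95% CI is the HR divided and multiplied by exp(1.96 x SE).

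| Events d | SE | CI factor |
|---|---|---|
| 2.5 | 1.26 | 11.9 |
| 5 | 0.89 | 5.8 |
| 10 | 0.63 | 3.5 |

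At 5 events, 80% power at two-sided 0.05 needs an HR of about exp((1.96 + 0.84) x 0.894) = 12.

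**4. Chance that no finite HR exists for one binary covariate** (no event in one level), at 10% in 50 patients:

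- 25/25 split: 0.9^25 = 0.0718; 1 - (1 - 0.0718)^2 = 0.138.
- 15/35 split: 0.9^15 = 0.2059 and 0.9^35 = 0.0250; 1 - (0.7941 x 0.9750) = 0.226.

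**5. Multivariate fits when nothing is truly predictive.** The document names no covariates, so their types are assumed: standard normal, or binary with 30% prevalence, with or without treatment arm. Other settings: 50 patients, 10% event rate by day 30, no losses, 2,000 simulated trials per setting. Unusable means no event, no convergence, or a log HR or its SE above 10 in absolute size. Extreme means any HR above 3 or below 1/3 (per SD for continuous covariates).

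| Covariates in the model | Unusable | Extreme, among usable |
|---|---|---|
| Two or three continuous, no arm | about 1-2% | about 13-18% |
| One continuous and one binary, no arm | about 23% | about 23% |
| Arm plus one to three others | about 14-52% | about 25-55% |

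Monte Carlo error is about 2 points, and repeat runs differ by a few points; two continuous covariates gave 11% extreme in one run. The 14% floor in the last row is the step 4 chance that one arm has no event.

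**6. Event rate doubled.** At 20%, arm plus three others gives 1-13% unusable and 18-45% extreme. Failed fits become uncommon; imprecision remains.

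**7. False significance.** With arm plus three others at 10%, some p < 0.05 appears in 8-11% of usable fits. Four independent tests would give 1 - 0.95^4 = 18.5%. There is no excess.

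**The case against.** The strongest reply is that this is a feasibility pilot, the Cox models serve a secondary aim, and section 11 says only that they will be examined. That stands as a limit on importance: nothing here touches the enrolment or follow-up objectives. Nor does section 11 say that the Cox models are how endpoints will be chosen; section 8 lists direct comparisons of outcomes for that aim. A reader might infer that the endpoint selection rests on these models, but the text does not assign them that role.

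Second, the failure rates depend on assumed covariates. This also stands. Section 11 speaks of clinical variables and does not name arm as a covariate, and many candidates in section 9 are continuous or nearly so (vital signs, injury severity, haemoglobin, platelets). With only such covariates, failed fits are rare. A reader might take the upper figures as bounds, or conclude that capping the model at two covariates could never help. Neither follows: two continuous covariates fit nearly always, while one continuous and one binary fail in about a quarter of trials. The confidence interval width in step 3 does not depend on this choice of model.

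Third, the 10% is an approximate adverse-effect rate. That is why 5% and 20% are shown.

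Fourth, section 14.4 lets enrolment run past 50. A reader might apply the 80% goal to obtain 50/0.80 = 62.5, so 63 patients and 6.3 events. But that goal is for 30 days, the extension is for three months, and no three-month retention is given. Even taken at face value, the CI factor would still be 4.8. Conversely, recording splenectomy both in hospital and at 30 days does not protect the count: one that occurs after discharge in a patient lost to follow-up is missed at both points.

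**Conclusion.** The concern holds as a weakness of a secondary analysis that should be corrected. On the document's own figures, about 5 splenectomies are expected, and 1 to 9 would be unsurprising. That is too few for a multivariate Cox model whose covariates are unnamed and unlimited and whose results sit beside a 0.05 threshold. Wide intervals are certain at this event count. Non-estimability is a risk, not a certainty: small with continuous covariates only, about a quarter with one continuous and one binary covariate, and up to about half with arm and several binary covariates.

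Two stronger conclusions are not supported. A reader might infer that the analysis would produce too many false-positive p-values; step 7 shows no excess. A reader might also infer that the trial's primary purpose is compromised; feasibility does not depend on these models.

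The conclusion assumes that the 10% in section 14.3.2 applies to this population over the follow-up period. At double that rate, failed fits become uncommon but the CI factor is still 3.5.

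**What to change.** In section 11, delete the multivariate Cox model and replace the sentence on Cox models with text such as:

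> Splenic salvage will be reported by randomised arm with exact 95% confidence intervals and a 95% confidence interval for the difference, alongside the planned chi-squared or Fisher comparison. Associations of salvage with at most three covariates, named here in advance, will be described one at a time by a Firth-penalised model with 95% confidence intervals: Cox if splenectomy dates are recorded, otherwise logistic regression for status at the stated horizon. These analyses are exploratory and no significance threshold applies to them.

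Section 9 lists secondary splenectomy but shows no date for it, although the list may be cut short in the copy reviewed. Recording the date would allow the penalised Cox version, which keeps partial follow-up time. If logistic regression is used, the text should also say how unknown status and death before the horizon are counted.

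Separately, sections 7.5 (30 days, plus or minus 3) and 14.4 (at least three months) must be reconciled so that salvage has one time horizon.

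The cost is wording only, plus a date field if it is not already captured; patients, visits and sample size do not change. There would be no multivariable predictor table. Estimates stay imprecise, because penalisation makes them finite but adds no information. In null simulations at 10% in 50 patients, single-covariate Firth logistic regression never failed and its intervals covered the true value in 97-100% of trials, yet a binary covariate still gave an odds ratio above 3 or below 1/3 in 25-27%. Hence the intervals must be shown and no threshold used. The salvage report would be modest too. With 2 and 3 splenectomies, for example, it would show 23/25 = 92% (74.0 to 99.0) against 22/25 = 88% (68.8 to 97.5), a difference of 4 points (Newcombe interval -14.7 to 22.9).

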1. PROTOCOL SUMMARY

Questions addressed

Our aim is to perform a randomized, prospective, pilot study comparing the use of coils versus vascular plugs for proximal splenic artery embolization in the setting of high-grade splenic trauma.

The questions addressed in this trial include:

1. Is it feasible to perform this type of study in this patient population by meeting patient accrual goals and obtaining adequate patient follow-up?
2. What are the clinical, technical, and economic outcomes associated with proximal splenic artery embolization using coils or vascular plugs?

Study population

Inclusion criteria: ≥18 years of age; trauma resulting in grade III or higher splenic injury on contrast-enhanced CT as defined by the AAST guidelines; splenic injury to be treated by non-operative management as decided by attending trauma surgeon and interventional radiologist; patient will undergo proximal splenic artery embolization as decided by the attending interventional radiologist

Exclusion criteria: inability to obtain informed consent; uncorrectable coagulopathy; patient is immunocompromised; pregnant; breast-feeding; non-English speakers; prisoners

Interventions

Patients will be screened for eligibility. Eligible patients will be referred for proximal splenic artery embolization and randomized to coils versus vascular plugs. Proximal splenic artery embolization will be performed. Relevant data from patient arrival and hospitalization will be collected. CT scan over-read will be performed by an attending abdominal radiologist. Follow-up data at approximately 30 days will be obtained (see

sections 6 “Patients, Recruitment, and Randomization”, 7 “Interventions”, and 9 “Data Collection”).

Outcome assessment

We plan to demonstrate the feasibility of performing this type of study in this patient population by meeting patient accrual goals and obtaining adequate patient follow-up. Secondarily, we will assess outcomes of both groups using technical success (ability to embolize the mid-splenic artery with the prescribed device), device failures, intra-procedural complications, procedural time, equipment costs, radiation exposure, need for secondary embolic agents, length of stay, post-embolization transfusion requirements, delayed complications, and splenic salvage rates as secondary endpoints.

Trial coordination

[name] and [name] will be principle investigators. [name] will be program manager.

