and larger than traditional coils, namely POD® coils (Penumbra, Alameda, CA, USA). Using these larger coils can decrease the number needed to obtain hemostasis. These coils come in two varieties: 1) a helical coil sized to the vessel diameter that anchors the coil pack in the high-flow vessel thereby reducing the risk of distal migration and 2) a packing coil that is used to fill in the spaces within the helical coil. A typical pSAE using coils will involve the deployment of one helical coil followed by multiple packing coils until hemostasis is achieved.

Vascular plugs attempt to overcome the limitations of coils. For example, the deployment of a single vascular plug can typically provide hemostasis in the mid-splenic artery, theoretically reducing procedural time, contrast load, and radiation exposure. Despite this, vascular plugs are usually less familiar devices to endovascular specialists. Another drawback of vascular plugs is that they cannot be deployed through a standard micro-catheter but rather require the advancement of a larger, stiffer 0.035 inch system into the mid-splenic artery. This may limit their use in very tortuous splenic arteries. Vascular plugs reaching up to 8mm in size (Amplatzer™ IV, Abbott Medical, Abbott Park, IL, USA) can be deployed through a standard 5F diagnostic catheter. Larger vascular plugs (Amplatzer™ II) require at least a larger 6F guiding catheter.

Currently, the selection of embolic agent for pSAE is primarily based on operator experience and preference. The efficacy, technical success, and cost of using coils compared to vascular plugs has been evaluated in such conditions as pelvic congestion syndrome [10], yet, to the best of our knowledge, these embolic agents have never been compared for their use in pSAE, much less in a randomized, prospective fashion. We anticipate this pilot trial to demonstrate the feasibility of a larger study and provide sufficient information to identify appropriate primary endpoints. The innovation of this proposal is strengthened by the inclusion of over-reads of pre-procedural CT scans, which will allow accurate grading of splenic injury and information regarding associated vascular injury to the spleen. If found, significant differences between our study groups in either clinical outcomes, technical parameters, or cost would have an immediate impact on how we care for trauma patients both locally and nationally.

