10. RECRUITMENT TARGETS

Our group performs approximately 100 SAEs in a 12 month period. Thus, we will consider having enrolled at least 50% of the SAE patients (50 patients total; 25 patients/arm) as success.

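### Section 11 gives Aim 2 only an unadjusted p<0.05 rule on about 11 outcomes at 25 per arm; estimates with 95% confidence intervals would serve endpoint identification better

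*Combined protocol and SAP*

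**What the plan says.** - **Purpose.** Section 4 gives Aim 2 as "To evaluate clinical outcomes in order to identify endpoints for a larger trial". Section 11 repeats it as a secondary aim: "we anticipate being able to identify potential variables as primary endpoints for a larger study". Section 3 has the same expectation: "We anticipate this pilot trial to demonstrate the feasibility of a larger study and provide sufficient information to identify appropriate primary endpoints".
- **Size.** Section 10 derives the target from accrual: "Our group performs approximately 100 SAEs in a 12 month period", and half of these is 50 patients, 25 per arm. No Aim 2 outcome enters the calculation.
- **Outcomes.** Section 1 lists technical success, device failures and intra-procedural complications, followed by "procedural time, equipment costs, radiation exposure, need for secondary embolic agents, length of stay, post-embolization transfusion requirements, delayed complications, and splenic salvage rates". That makes 11. Section 8 groups them slightly differently (4 clinical, 4 technical, 3 cost) and also reaches 11.
- **Analysis.** Section 11 uses Student's t-test for continuous variables and chi-squared or Fisher's exact test for categorical ones, with one rule: "A pre-determined p value of 0.05 was considered the threshold for statistical significance". It mentions no confidence intervals and no criterion for choosing an endpoint.
- **Covariates.** The only covariate models are for splenic salvage: "Both univariate and multivariate Cox models will be examined to determine the ability of clinical variables". Length of stay is therefore compared without covariates, although Section 9 collects AAST grade (initial CT report and over-read) and ISS.
- **Weight given to significance.** Section 3 says that, if found, "significant differences between our study groups in either clinical outcomes, technical parameters, or cost would have an immediate impact" on patient care locally and nationally.

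**The concern.** A pilot that is to inform endpoint choice needs to report how common each event is, how variable each continuous outcome is, and how uncertain the arm differences are. Section 11 instead asks of each outcome only whether p falls below 0.05. With 25 per arm that question can mislead in both directions: a chance difference in one of several outcomes may stand out, while a real difference in an infrequent event will usually be missed. A real difference that does reach significance will tend to be overstated. If significance, as the only rule on the page, came to guide endpoint choice, the larger trial could start from the wrong outcome or from an inflated effect.

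A smaller matter is precision. Injury severity plausibly explains some of the variation in length of stay, and the severity measures are already collected, but no arm comparison uses them.

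**Working it through.** **1. The plan's own figure.** 0.50 x 100 procedures = 50 patients; 50 / 2 = 25 per arm. This reproduces Section 10. It is a feasibility target; no effect size or power is stated, so there is no powered sample size to check.

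**2. Chance of at least one false positive.** The Section 1 list has five continuous outcomes (procedural time, equipment costs, radiation, length of stay, transfusion) and six naturally binary ones. Each t-test is taken at 5%. For the binary outcomes I assume rates of 1, 1, 3, 10, 10 and 20%, equal in both arms, and enumerate every possible table at 25 per arm. "Mix" below is chi-squared unless an expected count is below 5, otherwise Fisher.

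| Common rate | Actual size, Fisher | Actual size, mix |
|---|---|---|
| 1% | 0.0000 | 0.0000 |
| 3% | 0.0001 | 0.0001 |
| 10% | 0.0088 | 0.0100 |
| 20% | 0.0222 | 0.0443 |

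With independent outcomes, the family-wise chance is 1 - 0.95^5 x product of (1 - size) over the six binary outcomes.

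- Continuous outcomes alone: 1 - 0.95^5 = 22.6%.
- Binary outcomes alone: 3.9% (Fisher) or 6.3% (mix).
- Together: 25.7% (Fisher) or 27.5% (mix).

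With equal correlation between all 11 outcomes (20,000 simulations), the figures for Fisher / mix are 23.5% / 25.2% at 0.3, 20.2% / 21.7% at 0.5 and 16.9% / 18.4% at 0.7.

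**3. Power for an infrequent event.** Section 14.3.2 anticipates splenectomy for ineffective treatment in about 10%. It gives no rate by device, so 10% versus 20% is an assumption.

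- Smallest splits that reach p<0.05: 0 vs 6 (p = 0.022) and 1 vs 7 (p = 0.049); with chi-squared also 2 vs 8 (p = 0.034). In each case the gap is 6/25 = 24 points.
- Exact power: 8.6% (Fisher), 11.2% (mix).
- Mean absolute observed gap among significant results: 28.1 points (Fisher), 27.2 points (mix), against a true gap of 10.

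**4. What 50 patients can supply.**

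- An event rate: 5/50 = 10%, Wilson 95% CI 4% to 21%.
- A difference in rates: 2/25 vs 5/25 = 12 points, Newcombe 95% CI -8 to 32.
- A pooled SD: 95% limits of 0.83 to 1.25 times the estimate (48 df, normal data).
- A mean difference: 95% CI half-width t(48) x sqrt(2/25) = 2.011 x 0.283 = 0.57 SD.

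**5. Adjusting length of stay.** The share of variance (R2) explained by AAST grade and ISS is not in the documents; 0 to 30% is assumed. The normal case has a true difference of 0.8 SD. The log-normal case has log-SD 1.0, a 2.2-fold ratio, R2 on the log scale and raw means compared.

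| R2 | Normal: unadjusted | Normal: adjusted | Log-normal: unadjusted | Log-normal: adjusted |
|---|---|---|---|---|
| 0 | 79% | 77% | 59% | about 56-57% |
| 10% | 79% | 82% | 59% | about 59-60% |
| 20% | 79% | 86% | 59% | 63% |
| 30% | 79% | 90% | 59% | 67% |

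The gain is real at higher R2, close to nil at 10% with skewed data, and a loss of 2-3 points if the covariates are unrelated to stay.

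The choice of scale can matter more. In the same log-normal case a t-test on logs without covariates has about 79% power (raw t-test 60%). With gamma data (shape 1, 2.2-fold) the raw t-test does better, 73% against 58% on logs.

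**The case against.** The strongest reply is that the plan only names a threshold for significance. A reader might infer that endpoints will be picked by p<0.05, but no section says so; Sections 3, 4 and 11 speak only of identifying endpoints. That stands. What remains is that no other criterion is given and that Section 3 attaches importance to significant differences. That sentence is background motivation, so it is a matter of wording, not a decision rule.

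Second, feasibility is the primary outcome, and unadjusted secondary tests in a pilot are not an error. That also stands, and a stricter threshold would make things worse: at 0.05/11 = 0.0045, power for a 0.5 SD difference falls from 42% to 14% (normal approximation). The remedy is estimation, not multiplicity control.

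Third, a reader might quote 1 - 0.95^11 = 43% as the false-positive chance. That requires 11 independent tests each at exactly 5%. Fisher's test on infrequent events runs far below 5%, and technical success and device failures overlap heavily, so the planned tests do not behave that way.

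Fourth, one might predict that the larger trial would be far too small. Planning 80% power on the rates seen when 10% versus 20% happens to be significant would give 28-32 per arm instead of 199. The documents do not say how the larger trial will be sized, so this only illustrates overstatement.

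Fifth, arm means, SDs and counts are needed to compute the planned tests and would probably be reported. The clear gaps are the intervals and the basis for choosing endpoints.

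Finally, randomization already makes the unadjusted length-of-stay comparison unbiased. That is correct. Adjustment concerns precision only, and restricting entry to grade III and above limits what grade can explain.

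**Conclusion.** The concern holds in a moderate form. An unadjusted p<0.05 on about 11 outcomes at 25 per arm is poorly matched to identifying endpoints. The family-wise false-positive chance is about 26-28% with independent outcomes, or 17-25% with correlation of 0.3 to 0.7. It rests on assumed binary rates of 1-20% and comes mostly from the continuous outcomes. For splenectomy, 9-11% power and a minimum significant gap of 24 points rest on the anticipated rate of about 10% and an assumed 20% in the other arm.

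The documents do not support saying that endpoints will be selected by significance, that the larger trial will be mis-sized, or that the length-of-stay comparison is biased. The length-of-stay point is an optional gain in precision whose size depends on an unknown R2 and on skewness. The change is worth making because it is cheap; the primary feasibility outcome does not depend on it.

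**What to change.** In Section 11:

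1. For Aim 2, replace the 0.05 threshold with each arm's event rate, or mean and SD, and each arm difference with a 95% confidence interval, labelled exploratory.
2. State that endpoints for the larger trial will not be chosen on p<0.05 or on the observed difference, and name what will be used, for example event rate, SD and completeness of capture.
3. Optionally, add a comparison of total length of stay adjusted for AAST grade (over-read) and ISS, with the scale of analysis fixed in advance.

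Bring the Section 3 sentence on immediate impact into line with the pilot purpose stated in the same section.

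**Cost.** Plan wording and at most one regression; no new data or patients. The pilot would no longer declare significant device differences, and the intervals will be wide (about +/-0.57 SD for a mean difference). Adjustment loses about 2-3 points of power if the covariates are unrelated to stay.
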